SECONDARY: Microbial translocation [Primarily, Lipopolysaccharide binding protein (LBP)], zinc level, oxidative markers, safety measures (% subjects with >Grade 2 adverse events possibly or probably to study drugs), lipid levels, insulin resistance (HOMA-IR), endoPAT, and blood pressure.

Design and Outcomes:

This is a pilot open labeled randomized double arm study, studying the efficacy and safety of Zinc therapy on cardiovascular outcomes in ≥ 18 years old HIV-infected patients, on stable ART (for at least 12 weeks) and with zinc levels ≤ 0.75 mg/L in the last 60 days.

Subjects will be evaluated and data will be collected according to the following schedule:

Evaluation (Weeks)	Screen	Entry*	Wk 4	Wk 10	W 16 or premature study discontinuation
Written consent form	X				
Inclusion/exclusion	X				
Family history of CVD/diabetes/HTN		X			
CVD Risk Score		X			X
Targeted physical exam/weight/blood pressure	X	X	X	X	X
Compliance assessment/safety monitoring			X	X	X
Smoking, illicit drugs and alcohol status		X			X
Dietary logs and Activity status		X			X
Height	X				
Hematology/chemistries	X	X	X	X	X
Urine β -HCG (women)	X	X	X	X	X
Fasting lipoprotein profile		X			X
Fasting insulin, glucose, HOMA-IR		X			X
Plasma inflammation markers		X			X
Microbial translocation (IFAB, LBP)		X			X
Oxidative markers		X			X
Zinc levels	X	X			X
Calcium Score		X			
DEXA		X			
Endothelial function		X			X
Resting Energy Expenditure (REE)		X			X
Stored fasting plasma, serum, urine and stool ***	X	X	X	X	X

Intervention and Duration:

The duration of the study will be 16 weeks. Patients will be given zinc gluconate capsules at a dose of 45 mg, or 90 mg, elemental zinc daily for 16 weeks. No additional follow up will occur after 16 weeks.

Sample size and population:

The total sample size is 50 patients, 25 patients will be randomized to one (45 mg) capsules and 25 patients will receive two 45 mg capsules (or 90 mg).

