pharmacy. Only site pharmacists can access the randomization schedule at the time of the intervention assignment.

Blinding:

Patients will be unblinded to treatment allocation (1 versus 2 zinc gluconate capsules). The research nurse, responsible for providing the patient with zinc gluconate capsules will also be unblinded to treatment assignment. They will provide the patient with the capsules (1 or 2 capsules) and assess patient's adherence to the pills. Patient's treatment as well as adherence to pills (pills count) will be collected by the research nurse and kept in a locked electronic data sheet, only they have access to. Only the percent adherence to treatment (a percentage) will be shared with the rest of research team and entered in the shared electronic database.

The research assistant as well as the principle investigator will remain blinded to treatment assignment. The research assistant will be responsible to prepare DSMP reports with the principal investigator and will include enrollment and dropout rates, protocol deviations, subjects symptoms, review of clinical, laboratory results and percent adherence to treatment, while remaining blinded to treatment allocation.

The principle investigator, as well as the DSMP board will remain blinded throughout the conduct of the clinical trial unless unblinding is warranted to optimize management of an adverse event or for other safety reasons. In these specific circumstances, the research nurse will be responsible for breaking the blind to the principal investigator. This will occur in a private location to ensure the rest of the team remains blinded.

All statistical analyses will also be done in a blinded fashion. Data will be exported to the statistician as arm A versus arm B by the research nurse to preserve blinding. For analyzing adherence, they will also only have access to the percent as opposed to pill counts the research nurse uses to calculate this.

TIMING OF EVALUATIONS

Screening

All screening evaluations to determine eligibility must be completed within 30 days prior to study entry.

Entry

Evaluations must occur within 30 days after screening evaluations. If subject shows up ill with any acute symptom, the visit will be postponed until all symptoms resolved for at least 7 days.

On-Study Evaluations

Study visits must be scheduled on the weeks indicated in the schedule of events +/- 14 days.

Premature study discontinuation

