Subjects who stop study will undergo the premature study discontinuation evaluations as outlined in the Schedule of events under Week 16 visit. However if subjects stop study medication at any point during the study they will be asked to remain on study and continue to follow the procedures outlined.

DETAILED STUDY PROCEDURES BY VISITS

Screening: Before they enter, patients will be asked to visit the clinic at least once to be screened and ensure that they meet the requirements for entry into the study. Screening may take place on the same day as a normally scheduled clinic appointment, as long as subject is fasting. Before any tests can be obtained as part of this study, patients would have to decide whether or not they would like to participate in this study.

- If they choose to enroll, the informed consent form will be signed. The site investigator or a member of the study team will conduct the consenting process and a checklist indicating date and time the consent was signed, who was present, version date and if a copy was provided to participant will be filed in the subjects chart
- A targeted physical examination will be performed including height, weight and blood pressure
- Recent blood work will be reviewed to be sure that they meet the inclusion criteria. The HIV-1 RNA, and HIV testing to confirm HIV status will be obtained from the clinical chart as these are a part of routine care.
- Blood will be drawn for hematology/chemistries and zinc
- Plasma, serum, urine and stool will be collected and stored for potential future testing.
- For woman of reproductive potential, a urine sample will be taken for a pregnancy test.

If a participant does not meet inclusion criteria it will be noted in the chart with the reason for ineligibility.

If a participant meets the inclusion criteria and chooses to enroll, randomization will occur at the entry visit. The study team will notify the pharmacist which will allocate them with one of the two interventions according to the randomization schedule. Participants should start the intervention within two days of randomization allocation.

Study Entry: For entry visit, this will be fasting, as defined by no food or drink, except for plain water and medications for at least 8 hours. The following procedures will be done at entry.

- A medical history including family history
- Targeted physical exam including weight and blood pressure

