- For any Grade 4 toxicity (confirmed X 2 values for laboratory abnormalities) regardless of the cause, subjects will be taken off study drugs but will continue to be followed and undergo the evaluations as per schedule of events. Exceptions are asymptomatic elevation of indirect bilirubin in subjects receiving indinavir or atazanavir therapy, asymptomatic elevation of CPK, or elevations in lipid levels.

CRITERIA FOR PERMANENT STUDY DISCONTINUATION

-Request by the subject to withdraw

-At the discretion of the IRB

-Pregnancy or breast-feeding

[figure not shown]
-Request of the primary care physician if s/he thinks the study is no longer in the best interest of the subject.

STATISTICAL CONSIDERATIONS

The primary Aim of this pilot study is to demonstrate that oral dosing of zinc can impact a biological signature in patients with HIV. Biological signatures (hs-CRP, sCD14, sTNF-RI, LBP) will be assessed to determine if giving the natural product (zinc gluconate at 45 mg and 90 mg) to patients with HIV results in a meaningful change in the measure.

Inter-assay variability less than 15% are generally acceptable¹¹. To reduce this variability we will repeat each of these assays twice (run in duplicate) and compute average from the repeated assays performed in the same lab under same conditions conducted by the same technician. Given this set-up, the bioassays will efficiently quantify the biomarkers with less than 6% inter-assay variability which is substantially less than the general acceptable guidelines. Moreover, this inter-assay variability should be equivalent in both sets of measures obtained at baseline and after the Zinc supplementation.

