purpose of the study, the procedures to be followed, and the risks and benefits of participation. A copy of the consent form will be given to the subject, and this fact will be documented in the subject's record.

Subjects and Data Confidentiality

All laboratory specimens, evaluation forms, reports, and other records that leave the site will be identified by coded number only to maintain subject confidentiality. All records will be kept in a locked file cabinet. All computer entry and networking programs will be done with coded numbers only by study staff. Clinical information will not be released without written permission of the subject, except as necessary for monitoring by the IRB, FDA, or OHRP.

Recruitment plans

Subjects will be primarily recruited from the practice of the investigator (the Special Immunology Unit at University Hospitals Case Medical Center). All subjects seen at the Special Immunology Unit who meet the inclusion/exclusion criteria will be approached for study participation. In addition, subjects may be referred to the study by their primary care provider or their HIV provider from other HIV practices.

Study Discontinuation

The study may be discontinued at any time by the IRB as part of its duties to ensure that research subjects are protected.

Post-study Follow-up and Transition of Care

During the study period, the study subject will be encouraged to continue their routine regular follow up with their primary HIV care provider, whether in the Special Immunology Unit or in an outside HIV practice that referred them to the study. The study is not meant to replace the routine HIV care visits. After the study subject completes the study, he/she will continue to be followed by his/her primary HIV provider. There will be no additional follow-up for this study after the 16-week of the pre-defined study period. In addition, after the study subject completes the study, he/she will not be provided any further zinc supplements. If the subject primary care provider decides that it is in the best interest of the patient to be on zinc, he/she would be prescribed such supplements. The decision related to any follow-up or treatment after the study period will be left to the subject and his/her primary care provider.

BIOHAZARD CONTAINMENT

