Any detrimental change in a patient's condition subsequent to them entering the study and during the follow-up period should be considered an AE. When there is a deterioration in the condition for which the study treatment is being used, there may be uncertainty as to whether this is lack of efficacy or an AE. In such cases, unless the reporting physician considers that study treatment contributed to the deterioration or local regulations state to the contrary, the deterioration should be considered a lack of efficacy. Signs and symptoms of disease progression are therefore not considered AEs.

Serious Adverse Event

- A Serious Adverse Event (SAE) is an AE occurring during any study phase (eg, run-in, treatment, washout, follow-up), and at any dose of the investigational product, comparator or placebo, that fulfills one or more of the following criteria:
 - Results in death
 - Is immediately life-threatening
 - Requires inpatient hospitalization or prolongation of existing hospitalization
 - Results in persistent or significant disability or incapacity
 - Is a congenital abnormality or birth defect
 - Is an important medical event that may jeopardize the patient or may require medical intervention to prevent one of the outcomes listed above.

Any event or hospitalization that is unequivocally due to progression of disease, as determined by the investigator, must not be reported as an SAE.

The causality of SAEs (their relationship to all study treatment) will be assessed by the investigator(s)

Reporting of Adverse Events

When recording/reporting AEs, the use of diagnoses is preferred (when possible) to recording/reporting a list of signs and symptoms. However, if a diagnosis is known and there are other signs or symptoms that are not generally part of the diagnosis, the diagnosis and each sign or symptom will be recorded/reported separately.

Illiterate Subjects

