Pregnancy : Zinc may not be safe for unborn babies. If patients are having sex that could lead to pregnancy, they must agree not to become pregnant or make a woman pregnant. Because of the risk involved, patients and their partner must use two methods of birth control that they discuss with the study staff. They must continue to use both methods until 6 weeks after stopping study drug. They may choose two of the birth control methods listed below:

- Birth control drugs that prevent pregnancy given by pills, shots, intra-vaginal ring or placed on or under the skin
- Male or female condoms with or without a cream or gel that kills sperm
- Diaphragm or cervical cap with a cream or gel that kills sperm
- Intrauterine device (IUD)

If women can become pregnant, they must have a pregnancy test before they enter this study. The pregnancy test must be negative. In addition, is study subjects think they may be pregnant at any time during the study, they are to tell the study staff right away. In the event that a patient becomes pregnant while on study, they will be taken off study, and no further evaluations or tests will be performed as part of the study.

Zinc Supplementation: At the doses used, uncommon side effects include nausea, vomiting, and abdominal pain (gastritis). At higher doses and when used for a long periods (years), copper deficiency

and related anemia may happen. This is extremely unlikely since we are only giving 45 mg or 90 mg daily for up to 16 weeks. Such doses have been shown to be safe even when given for 12 months to elderly frail subjects. In addition, in diseases such as Wilson's disease, zinc is given at a dose of 50 mg three times daily for prolonged durations. We will closely monitor subjects who will receive blood draws for chemistries, hematology and liver enzymes.

OTHER RISKS: Patients are informed to tell their study doctor or study nurse about all other drugs they are currently taking including non-prescription medications, alcohol, recreational, and herbal products. These drugs, if taken with the study medication, can result in dangerous interactions. If patients have questions about the drug that will be used in this study and the potential for interaction with other drugs that they take, they are instructed to ask their study doctor to provide additional information.

In addition to the risks and discomforts listed here, there may be others that are currently not known.

BIBLIOGRAPHY REFERENCED

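### Participants who become pregnant leave the study with no outcome follow-up, so the birth-defect SAE criterion has no planned data source

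*Combined protocol and SAP*

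**What the plan says.** All references are to the combined protocol and SAP.

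- **Risks and Discomforts, pregnancy paragraph.** It warns of possible harm to a fetus. Two contraceptive methods are required until 6 weeks after the last dose, and a participant must tell staff promptly if she suspects pregnancy during the study. If she becomes pregnant, "they will be taken off study, and no further evaluations or tests will be performed as part of the study".
- **Criteria for Permanent Study Discontinuation.** The list includes "Pregnancy or breast-feeding".
- **Intervention and Duration (précis).** "No additional follow up will occur after 16 weeks".
- **Post-study Follow-up and Transition of Care.** "There will be no additional follow-up for this study after the 16-week of the pre-defined study period". Later care is left to the participant and her primary care provider, and no return of information to the study is described.
- **Serious Adverse Event.** An SAE "is an AE occurring during any study phase (eg, run-in, treatment, washout, follow-up"), and one of its criteria reads "Is a congenital abnormality or birth defect".
- **Premature study discontinuation.** The general rule is "Subjects who stop study will undergo the premature study discontinuation evaluations as outlined in the Schedule of events under Week 16 visit".
- **On-Study Evaluations.** "Study visits must be scheduled on the weeks indicated in the schedule of events +/- 14 days".
- **Schedule of events.** Urine pregnancy tests and hematology/chemistries are marked at the same visits: Screening, Entry and Weeks 4, 10 and 16.

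**The concern.** The protocol treats fetal exposure as a real risk: it requires a negative test before dosing, two contraceptive methods that continue after the last dose, and a birth-defect criterion among the SAEs. Its instruction for an actual exposed pregnancy is then to stop observing. By contrast, under Toxicity Management a participant taken off zinc for a Grade 4 toxicity stays on the visit schedule.

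At stake is safety information. If an exposed pregnancy occurred, the study's own rules would give the IRB and the DSMB nothing planned to review about how it ended. A participant who reports a pregnancy between visits would also have no study safety bloods after her report.

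**Working it through.** The plan states no figure on this point, so there is none to reproduce. The check is a timeline, with Week 0 = Entry.

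**Inputs from the protocol**
- Negative pregnancy test within 72 hours before study drug (Inclusion Criteria).
- Visits at Weeks 4, 10 and 16, each ±14 days.
- Contraception until 6 weeks after the last dose.
- 25 participants per arm; power calculated on 20 per dose.

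**Assumptions, not in the protocol**
- Birth 35 to 40 weeks after conception.
- The pre-dose test could miss a conception up to 2 weeks before Entry.
- Dosing could run to a late Week 16 visit.

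**1. Can a term birth fall inside the study?**
- Latest last visit: 16 + 2 = Week 18.
- Conception at Entry: 18 weeks past conception at that visit. Shortfall: 35 − 18 = 17 to 40 − 18 = 22 weeks.
- Conception at Week −2, missed by the test: 18 + 2 = 20 weeks past conception. Shortfall: 35 − 20 = 15 to 40 − 20 = 20 weeks.

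So the last visit is at least 15 weeks short of a term birth, even for a participant who was never taken off study. The SAE definition requires an event within a study phase, and no phase reaches that date.

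**2. How old are the last safety labs?**
- Pregnancy found by a scheduled test: hematology/chemistries are scheduled at the same visit, so nothing is lost.
- Pregnancy reported between visits, nominal schedule: the longest gap is 10 − 4 = 6 or 16 − 10 = 6 weeks.
- At the window limits: 12 − 2 = 10 or 18 − 8 = 10 weeks.

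**3. When would an outcome contact fall?**
- Earliest term birth: −2 + 35 = Week 33, which is 33 − 16 = 17 weeks after Week 16.
- Latest: last dose at Week 18, conception 6 weeks later at Week 24, birth at 24 + 40 = Week 64, which is 64 − 16 = 48 weeks after Week 16.
- A miscarriage or termination could be known earlier.

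**4. Effect on the primary analysis**
- Inflammation markers are scheduled only at Entry and Week 16, so an exit before Week 16 leaves no scheduled post-baseline value.
- Each such exit costs 1/25 = 4% of an arm, against a margin of 25 − 20 = 5 over the number used for power.
- The number of pregnancies cannot be derived, because the number of women of child-bearing potential is not given.

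**The case against.** The strongest reply is that this argues from silence. The consent pages, a natural home for a pregnancy follow-up clause, have been removed, and a figure is missing beside the discontinuation criteria. That limits the claim to the text available. It does not cancel the explicit rules, which end evaluations on pregnancy and end follow-up at 16 weeks.

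Second, a reader might infer that the study could learn an outcome only by chance. The documents do not support that. Recruitment is mainly from the investigator's own clinic, the study already draws HIV-1 RNA and CD4 counts from the clinical chart, and participants must report a suspected pregnancy. Asking about an outcome is also not clearly an evaluation or a test. For the clinic's own patients the route is informal rather than absent; it is weaker for those referred from outside practices. What stands is that no route is planned.

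Third, a reader might see a contradiction with the rule that gives early leavers the Week 16 evaluations. The pregnancy sentence is better read as a specific exception to that rule. A cross-reference would be tidy, but its absence is editorial.

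Fourth, one might press for the lost efficacy data and ask for a biomarker draw at exit. The protocol excludes pregnancy and postpones visits for acute illness to protect these markers. A value taken in pregnancy could confound the primary endpoint, and the loss is too small to justify it.

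Finally, materiality is low: this is a 50-person, 16-week pilot with double contraception. That is a reason to keep the remedy small.

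**Conclusion.** The point holds as a low-cost safety improvement. Under the stated rules, a term outcome of a zinc-exposed pregnancy falls at least 15 weeks after the last possible visit, so the birth-defect SAE criterion has no planned data source for a participant's own pregnancy. The figure rests on birth 35 to 40 weeks after conception and on a conception at most 2 weeks before Entry being missed. The conclusion is the same across that range.

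A secondary gap is that safety labs could be up to 6 weeks old (10 at the window limits) when a pregnancy is reported between visits.

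The point says nothing against the sample size or the primary analysis, where the effect is negligible. Nor does it show that the consent form lacks a follow-up clause. Follow-up of partners' pregnancies is a separate question and is not argued here.

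**What to change.** 1. In the pregnancy paragraph of Risks and Discomforts, replace the ban on further evaluations and tests with: *zinc is stopped; safety hematology/chemistries are drawn with her consent if none were taken at the visit that detected the pregnancy; and, with her consent, the pregnancy outcome is obtained by one chart or telephone contact and reported to the IRB and DSMB.*
2. Name this as an exception in Intervention and Duration and in Post-study Follow-up and Transition of Care.
3. In the Serious Adverse Event section, state that a birth defect learned this way counts as an SAE although it is found after Week 16.
4. Ask participants to report any pregnancy conceived within 6 weeks after the last dose. The last scheduled test is at Week 16, so this part relies on self-report.

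No biomarker draw and no partner follow-up are needed.

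**Cost.** Protocol and consent wording, at most one safety blood draw, and one contact per known participant pregnancy. For a term birth that contact falls about 17 to 48 weeks after Week 16, so the promise of no further follow-up would no longer hold for these few participants.
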